1 SYNOPSIS

NAME OF THE SPONSOR:

ZipLine Medical, Inc. [name] USA

CLINICAL INVESTIGATION TITLE:

A randomized, controlled, post-market clinical investigation to evaluate Zip Surgical Skin Closure Device in comparison of using Standard of Care sutures for Laceration Repair in Pediatrics in a Pedaitric Emergency Medicine Department

CLINICAL INVESTIGATION CODE:

INVESTIGATIONAL DEVICE:

Zip® 4 Surgical Skin Closure Device

AIM:

To evaluate the Zip 4 Surgical Skin Closure Device in a pediatric population requiring laceration repair in an Emergency department.

OBJECTIVES:

Primary Objective

- The primary objective of this clinical investigation is to evaluate the time and costs savings of the Zip 4 Surgical Skin Closure Device in comparison to conventional sutures used in a pediatric population presenting for laceration repair.

Secondary Objective

- The secondary objective of this clinical investigation is to evaluate the satisfaction and outcomes of the Zip 4 Surgical Skin Closure Device in comparison to conventional sutures used in a pediatric population presenting for laceration repair.

OVERALL CLINICAL INVESTIGATION DESIGN:

A prospective, randomized, controlled post-market clinical investigation that will enroll pediatric subjects requiring laceration repair. The investigation population will consist of 30 subjects fulfilling the eligibility criteria for the clinical investigation. The subjects will be randomly assigned at a 1:1 ratio to either the Zip 4 Surgical Skin Closure Device group or the Standard of Care sutures group. The duration of the investigation is estimated to 6 months, including a 5-month recruitment period and 1-month follow up period.

INCLUSION AND EXCLUSION CRITERIA:

Inclusion Criteria

The subjects have to meet all of the following criteria to be eligible to participate in the clinical investigation:

- 1. Between 4 to 18 years of age at the time of laceration repair.
- 2. Require suture closure as standard of care for simple straight wounds on trunk or extremities or face up to 4 cm long.
- 3. Low Tension Laceration, e.g. skin can be easily approximated by pinching with fingers.
- 4. Subject and legal representative(s) are willing and able to comply with the investigational device removal and meet the follow up visit requirements.
- 5. Subject and legal representative(s) have been informed of the nature, the scope and the relevance of the study.
- 6. Subject and legal representative(s) have voluntarily agreed to participation and have duly signed the Informed Consent Form.

Exclusion Criteria

Subjects meeting any of the following criteria will not be permitted to participate in the clinical investigation:

- 1. Known personal or familial history of scar hypertrophy.
- 2. Known or suspected allergies or hypersensitivity to non-latex skin adhesives.
- 3. Atrophic skin deemed clinically prone to blistering.
- 4. Wounds that are easily susceptible to infection as a result of exposure to unsanitary conditions ("dirty wounds").
- 5. Wounds that require deep dermal closure using sutures.
- 6. Known or suspected mental problems and/or aggressiveness that indicates that the subject might try to remove the device during the treatment period.
- 7. Participating in any other clinical investigation.
- 8. Known health condition that would affect healing in the opinion of the investigator.
- 9. Any subject that according to the Declaration of Helsinki is deemed unsuitable for study enrolment.

PERFORMANCE AND SAFETY ENDPOINTS:

Primary Endpoint (performance)

The primary endpoint in this clinical investigation is the mean difference in time to wound closure for the two treatment methods used. These include total treatment time and duration of period starting from the preparation of procedure until protective wound dressing is applied, and including whether or not sedation was used when comparing the Zip 4 Surgical Skin Closure Device and the Standard of Care closure suturing.

Secondary Endpoints (performance)

- Difference in Wound Evaluation Score at 10 days and 30 days post-treatment compare to baseline when comparing scar satisfaction and appearance of the subjects receiving Zip 4 Surgical Skin Closure Device versus Standard of Care closure suturing. The score will be based on digital photographs taken on day 0, day 10 and day 30 and made by an independent panel of blinded physician(s).
- Rate of wound healing satisfaction in subject at 30 days post-treatment when comparing Zip 4 Surgical Skin Closure Device versus Standard of Care closure suturing. The endpoint will utilize a questionnaire for the subject to fill out.
- The level of pain in connection to device application and removal measured by a visual analog scale (VAS) 0-100 mm.

Secondary Endpoint (safety)

- The incidence and severity of adverse events associated with the Zip 4 Surgical Skin Closure Device and Standard of Care closure sutures.

STATISTICAL METHODS:

Performance Analysis and Safety Analyses

Statistical analysis on variables of interest, include subject demographics, baseline characteristics, effectiveness and safety endpoint (adverse events), will be summarized descriptively by randomization arm. A "t" Test will be applied for testing the Hypothesis of the two closure methods, including "p" values for statistical significance. Mean, standard deviation, range, and Coefficient of Variation (CV) will be reported for closure times for both the two closure treatment methods of Suture and Zip for the primary endpoint. For the secondary endpoints, mean, standard deviation, range, and Coefficient of Variation (CV) will be reported for the VAS scale data. Additional analysis will be reported per the attribute satisfaction survey criteria obtained from subject satisfaction data at the 30 day follow-up interval. This will include an analysis of Average Satisfaction Scores, summary statistics, plus a histogram analysis comparing subject satisfaction data for both treatment groups of SoC sutures and Zip 4 device.

2 TAE	LE OF CONTENTS	
1 SYN	OPSIS	2
2 SPC	NSOR CIP APPROVAL PAGEERROR! BOOKMARK NOT	DEFINED.
3 TAI	BLE OF CONTENTS	
4 DEI	FINITIONS AND ACRONYMS	7
5 INT	RODUCTION	
5.1	Background	8
5.2	Clinical data	
6 IDE 6.1	NTIFICATION AND DESCRIPTION OF THE INVESTIGATIONAL DEVICE Manufacturer	
6.2	Identification of clinical investigational medical device	12
6.3	Device accountability/traceability	12
6.4	Intended purpose	12
6.5	Indication and population	12
6.6	Manufacturing and materials	13
6.7	Training and experience	13
6.8	Installation and use	13
7 JUS	TIFICATION OF CLINICAL INVESTIGATION DESIGN	14
8 RIS	KS AND BENEFITS OF THE INVESTIGATIONAL DEVICE AND CLINICAL	
8 RIS INVEST	KS AND BENEFITS OF THE INVESTIGATIONAL DEVICE AND CLINICAL GATION	16
8 RIS INVEST 8.1	KS AND BENEFITS OF THE INVESTIGATIONAL DEVICE AND CLINICAL GATION Anticipated clinical benefits	16 16
8 RIS INVEST 8.1 8.2	KS AND BENEFITS OF THE INVESTIGATIONAL DEVICE AND CLINICAL GATION Anticipated clinical benefits Anticipated risks with the device	16 16 16
8 RIS INVEST 8.1 8.2 8.3	KS AND BENEFITS OF THE INVESTIGATIONAL DEVICE AND CLINICAL GATION Anticipated clinical benefits Anticipated risks with the device Residual risks	16 16 16 16

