7.1 Anticipated clinical benefits

The potential benefits of the Zip device over standard of care closure include:

- Improved cosmetic outcome
- Greater patient satisfaction
- No skin piercing
- Reduced procedure time
- Rapid one-person closure time
- Eliminate need for skin sutures
- Improved staff safety reduced needle stick

The investigation is intended to measure the result of some or all of these benefits.

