7.3 Residual risks

The residual risks that may occur include:

- The development of post-operative edema may cause skin shearing, skin blistering or loss of adhesion to occur.
- Application of any surgical tape or adhesive skin closure may result in skin stripping upon removal.
- As with all adhesive products applied to the skin, a small percentage of individuals may experience allergic reaction and/or hypopigmentation or hyperpigmentation following removal.
- The effect of petroleum-based ointments when used in conjunction with this device is unknown.
- Do not use if device becomes damaged during the procedure. Risk of device failure if device is damaged.

- Single use device. Do not reuse. Risk of device failure or infection if reused.

The described residual risks are understood risks associated with a non-invasive device intended for the closure of wounds.

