9.1 General

This is a prospective, randomized, controlled post-market clinical investigation to compare the use of Zip 4 device to standard of care skin closure sutures in pediatric subjects requiring laceration repair. 30 subjects will be recruited

The investigation consists of one screening/baseline visits at day 0 and 2 follow ups at day 10 and day 30 (*Figure 4*). After written informed consent has been acquired at the screening/baseline visit the subject will be evaluated and checked for eligibility by a pediatric emergency physician with clinical experience and expertise in laceration repaiar . An eligible subject will be randomized (1:1) to either test or SoC group. Subjects in the test group will be treated with the Zip 4 device, and subjects in the SoC group will instead be treated with conventional sutures as wound closure. After treatment, the subject is scheduled for follow up 10 days and 30 days post-treatment. At day 10 follow up study personnel will remove the Zip device or sutures. During both follow up calls at day 10 (after removal of device) and day 30, the subjects are assessed for the outcome of the laceration repair though subjects interviews and questionnaires filled out by the subject with help of their legal representative(s), if necessary. In addition, a blinded panel of 2 independent plastic surgeons will evaluate the cosmetic outcome of the laceration repair by reviewing digital photographs taken at screening/baseline visits versus 10 days and 30 days follow up.

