9.3 Secondary endpoints (performance)

- Difference in Wound Evaluation Score at 10 days and 30 days post-treatment compare to baseline when comparing scar satisfaction and appearance of the subjects receiving Zip 4 Surgical Skin Closure Device versus Standard of Care closure suturing. The score will be based on digital photographs taken on day 0, day 10 and day 30 and made by an independent panel of blinded two specialists in plastic surgery.
- Rate of wound healing satisfaction in subject at 30 days post-treatment when comparing Zip
 4 Surgical Skin Closure Device versus Standard of Care closure suturing. The endpoint will
 utilize a questionnaire for the subject when possible or his caretakers to fill out.
- The level of pain in connection to device application and removal measured by a visual analog scale (VAS) 0-100 mm.

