9.8 Clinical Investigation Procedures

9.8.1 Schedule of clinical investigation procedures/assessments

The assessments and procedures that will be performed during the clinical investigation are illustrated in *Table 3* below.

Study assessment	Visit 1 Day 0	follow-up 1 Day 10 (+/- 2 days)	follow-up 2 Day 30 (+/- 2 days)
Study information	Х		

Informed consent	Х		
Demographics	Х		
Relevant Medical and Surgical history	Х		
Physical examination (Type, size, location of laceration)	Х		
Inclusion/Exclusion criteria	Х		
Randomization	Х		
Wound preparation, e.g. cleansing ¹	Х		
Local Anesthesia and/or Sedation ²	Х		
Device application ³	Х		
Dressing application	Х		
Study participant instructions ⁴	Х		
Device and dressing removal ⁵		X	
Photographs taken ⁶	Х	X	Х
Visual Analog Scale (VAS)	Х	X	
Wound healing satisfaction questionnaire			X
Subject interview		Х	Х
Adverse event	Х	Х	Х
Medical review / Concomitant medication	Х	Х	Х
Study Exit			Х

¹ According to clinical routine.

² According to clinical routine. Zip group: Anesthesia and/or sedation only use if deemed necessary by Investigator. Document in Concomitant Medication Log.

³ Test group will be treated with Zip 4 device and SoC group with conventional sutures as wound closure.

⁴ Instructions prior discharge regarding post-treatment and additional follow up visits.

⁵ suture ir device removal will be conducted at FU session 1 at the PED or at home by a member of staff of the study

⁶ Photographs will be taken at the wound area during Visit 1 and follow up visits by the site personnel, . Please be aware of not adding any personal numbers or identifying characteristics on the photographs, only subject identification number and visit information.

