9.8.1.2 Follow up 1 (Day 10 +/- 2 days)

At the first follow up the device, either Zip 4 device or SoC sutures will removed at day 10(+-2 days). Prior discharge at visit 1 the subjects will receive instructions that if:

- 1) Treated with Zip 4 device the subject and their legal representative(s) will remove the subject themselves at day 10. If necessary, the subject/legal representative(s) may call the A&E for assistance during the removal.
- 2) Treated with SoC sutures the subject and their legal representative(s) will visit the Pediatric Emergency Department or at home for removal of the sutures. During the follow up after device removal the subject will be asked about any adverse events that may have occurred, and a review of the concomitant medication. The subject will be interviewed about the usage of the device, and will fill out the questionnaire, VAS, and photograph the laceration. Next follow up day 30 will be scheduled if not done at visit 1.

All of the above can be done in assistance by the legal representative(s), if needed.

The following assessments/procedures will be performed at follow up 1:

- Subject interview
- VAS
- Cosmetic Outcome
 - High definition photos will be taken of the laceration
 - Registration of any Adverse Events
- Registration of Concomitant Medication

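### The wound score is called blinded, but the photograph rules let readers link a child's day-10 image to the day-30 score, with no safeguard stated

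*Protocol*

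**What the plan says.** Section 9.6.4 states that the trial is open to investigator and subject. The WES is the one outcome for which blind assessment is claimed. The Synopsis describes a score from "digital photographs taken on day 0, day 10 and day 30 and made by an independent panel of blinded physician(s", and sections 9.1 and 9.3 specify two plastic surgeons. The endpoint in section 9.3 is the "Difference in Wound Evaluation Score at 10 days and 30 days post-treatment compare to baseline".

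The provisions that bear on the blinding are these:

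- **Reading.** Section 9.1 has the panel "reviewing digital photographs taken at screening/baseline visits versus 10 days and 30 days follow up".
- **Labelling.** Footnote 6 to Table 3 (section 9.8.1) tells site staff to keep personal identifiers off the photographs and to put on them "only subject identification number and visit information".
- **Timing.** Section 9.8.1.2 describes the follow-up after removal, at which the subject "will fill out the questionnaire, VAS, and photograph the laceration". The day-0 photograph is taken before closure (section 9.8.1.1).
- **Traces.** Section 7.1 lists "No skin piercing" among the benefits of Zip. Section 7.3 warns: "Application of any surgical tape or adhesive skin closure may result in skin stripping upon removal".
- **Late removal.** Section 5.8 lets the physician leave the device on past the day-10 visit.

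**The concern.** Blind reading of a scar depends on what the reader sees and in what order. If the day-10 picture shows puncture points, an adhesive outline or the device itself, the reader may infer how the wound was closed. If the same reader can then tell which day-30 picture belongs to that child, the day-30 score is no longer given in ignorance of the treatment.

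Several of the six WES items call for judgement, overall cosmesis and contour among them, so a preference for one method could move the score. Section 8.4 lists physician satisfaction with scar outcome among the things the secondary endpoints will verify. A difference reported as blind could therefore partly reflect reader opinion.

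**Working it through.** There is no stated figure to reproduce, so the check sets the provisions side by side.

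1. **Does any image show the closure?** The day-0 image cannot, because it precedes application. The day-10 image can, because it follows removal. The sentence in section 9.8.1.2 that places the photograph after removal runs on from the item on sutures. However, the assessment list below it covers both arms, and the CRF page for follow-up 1 also puts device removal ahead of photography. The phrase in section 9.1, "During both follow up calls at day 10 (after removal of device) and day 30", points the same way, but it governs interviews and questionnaires, so the timing of the photograph rests on section 9.8.1.2.

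2. **Would the two arms look different?** Sutures puncture the skin and Zip does not (7.1). Adhesive may strip skin on removal, or be followed by pigment change (7.2, 7.3). Where the device stays on past the visit (5.8), a day-10 image could show it in place. None of these sections describes photographs, so recognition by a plastic surgeon is a reasonable inference and not a documented fact.

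3. **Can a reader connect the day-10 and day-30 images of one child?** Yes, if the files reach the panel as footnote 6 has them labelled. The subject number ties the images together and the visit label says which is which. The comparative review in section 9.1 points in the same direction. On the CRF form, the baseline, follow-up 1 and follow-up 2 blocks stand in sequence.

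4. **Does anything break the link?** The protocol states no recoding of images, no random or separate reading order, and no lock on the day-30 score before the day-10 image is seen.

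5. **Does the change-from-baseline definition require readers to see linked images?** No. Each image can be scored on its own and the difference formed at analysis. The link is needed in the data set, not at the reading screen.

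6. **How large could the effect be?** Six items scored 0 or 1 give a total of 0 to 6, so one item judged differently moves one child's score by 1 point. The protocol gives no standard deviation for the WES, no expected difference and no rate of reader error, and section 11.1 names no test for it. The calculation stops there.

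**The case against.** The strongest reply is that much of this is operational detail. Footnote 6 is a privacy instruction to site staff and does not say that readers receive files so labelled. Recoding and reading order often sit in a reading manual. That is fair as far as it goes, but no such manual is mentioned, and what the protocol does prescribe is the label and the comparison, both of which favour linking.

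Four stronger readings are tempting and are not supported:

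- **The panel reads each child's three images in one sitting.** The CRF form has a separate evaluation date for each time point, so separate readings are possible. Labels would still link images across sittings.
- **The label itself gives away the arm.** It does not. The subject number is assigned at consent, before randomisation, and differs from the randomisation number (9.6.4, 9.8.1.1).
- **The day-10 picture is taken immediately after removal.** No interval is stated. The protocol also disagrees on who removes Zip: study personnel in sections 9.1 and 9.8.1.1 and footnote 5, the family in section 9.8.1.2. Those passages must be reconciled.
- **The false-positive rate is raised by a calculable amount.** One could assume a standard deviation, a reader shift and a t test, but section 11.1 names t tests for the hypothesis statements and the pain scale, not for the WES. Any rate so obtained would describe the assumptions and not this trial.

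Two further limits stand. Visible marks show the closure used, which may differ from the allocation, because section 5.8 allows a poor Zip result to be replaced by sutures. Stitch marks may also still show at day 30, so no reading order makes the blinding certain.

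**Conclusion.** The point holds in a limited form. As written, the plan lets knowledge of the closure method, inferred at day 10, reach the day-30 score, and it states nothing to prevent this while calling the assessment blinded. The route is carry-over from day 10; pairing baseline with day 30 alone adds nothing, since the baseline image shows no closure.

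The conclusion assumes that experienced readers can sometimes recognise puncture or adhesive traces, and that images reach them as labelled. The size and direction of any bias cannot be computed from the protocol. The primary endpoint, procedure time, is untouched. This is a worthwhile, cheap improvement to a secondary endpoint and does not threaten the trial. It has to be made before reading starts, because a reader who has recognised the closure cannot be blinded again.

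**What to change.** Amend the Synopsis, sections 9.1 and 9.3, and footnote 6 as follows:

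- Keep subject number and visit on the site's own files. Give readers copies under a random code that carries neither, shuffled across children.
- Score and lock the day-30 images as a separate set before any day-10 image is read. This step matters most, because the site and shape of a wound can link images even without a label.
- Join scores to subject and baseline only at analysis, where the change from baseline is formed.
- Describe the WES as assessed by readers not told the allocation, and state that blinding is not assured, particularly at day 10. Do not present day 30 as fully blinded either.
- Do not crop away skin around the wound to hide adhesive marks; the inflammation item needs it.

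The cost is protocol wording and some file handling, with no extra visit or reader. The remaining weakness is that residual stitch marks may still reveal the closure at day 30.

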3 DEFINITIONS AND ACRONYMS

ADE	Adverse Device Effect
AE	Adverse Event
ASADE	Anticipated Serious Adverse Device Effect
CA	Competent Authority
CIP	Clinical Investigation Plan
CIR	Clinical Investigation Report
CV	Coefficient of Variation
CRF	Case Report Form
CRO	Contract Research Organization
DEHP	di-(2-ethylhexyl)phthalate
DD	Device Deficiency
DMC	Data Monitoring Committee
DMP	Data Management Plan
DMR	Data Management Report
DVP	Data Validation Plan
EEA	European Economic Area
EU	European Union
FAS	Full Analysis Set
FDA	Food and Drug Administration
ICF	Informed Consent Form
IEC	Independent Ethics Committee
ISO	International Organization for Standardization
MDD	Medical Device Directive
PI	Principal Investigator
PIS	Patient Information Sheet
PPS	Per Protocol Set
Residual Risk	Risk remaining after risk control measures has been taken
SADE	Serious Adverse Device Effect
SAE	Serious Adverse Event
SAP	Statistical Analysis Plan
SD	Standard Deviation
SDV	Source Data Verification
SoC	Standard of Care
SOP	Standard Operating Procedure
USADE	Unanticipated Serious Adverse Device Effect
VAS	Visual Analog Scale
Zip device	Zip Surgical Skin Closure Device
WMA	World Medical Association

4 INTRODUCTION

4.1 Background

Every year a significant number of lacerations are managed at the Pediatric Emergency Room (1). Lacerations require proper skin closure in order to heal properly with good cosmetic outcome. Sutures are a common method for laceration closure [2]. With proper preparation of the wound, skilled procedure and compliant post-procedure wound care, outcomes tend to be favorable with good cosmetic outcome. Nevertheless, suturing takes significant time and may require a high degree of skill and experience [3]. The application of sutures may require multiple injections of anesthesia into the wound site, which may cause anxiety in patients, particularly in children [4]. For a child, the thought of needles and sutures may be worse than the actual injury itself. In some cases, pediatric patients may require sedation to reduce anxiety. In the patient-centered health care, it is a matter of course to increase patient satisfaction. One step in this direction might be to replace suturing with non-invasive methods.

According to current clinical routines, suturing should in most cases be performed by physicians [5]. It therefore takes significant resources (time and personnel) to treat a laceration. From diagnosis, consultation, anesthesial injections and sedation (if required) until suturing, it can take more than one hour. Pediatric emergency departments often have a stressful environment with many patients to treat and it would be valuable if this process could be shortened. In addition, treated children may prefer to remove the sutures at a clinic even if it is usually not required with a follow up visit. This additional visit takes time for the medical staff, the child and the parent/guardian. Hence, a faster and more efficient treatment might reduce time and resources, allowing more patients to be treated at the Emergency departments.

ZipLine Medical, Inc. has developed a novel, non-invasive skin closure device called "Zip Surgical Skin Closure Device" (Zip device) as an alternative to conventional sutures, staples and glue for closure of the skin for surgical incisions or laceration repair. The Zip device is a single use, sterile medical device that is designed to provide closure speed superior to sutures, while resulte in a suture-like cosmetic outcome [6]. Feedback from post-market surveillance and evidence from published clinical studies suggest that these design intentions are correct [7].

The Zip device has been commercially available since April 2013, with over 100.000 clinical cases in 30 countries in orthopedics, electrophysiology, dermatology, plastic and reconstructive surgery, vascular surgery, obstetrics and gynecology, and emergency medicine. Thus, the Zip device is not restricted to any particular procedure, and not either to a patient population. Randomized clinical investigations using the Zip device for skin closure in pediatric patients [6] as well as elderly patients [8] have demonstrated good clinical outcome.

Not only has previous studies showed to reduce the time in wound closure, but also that the Zip device is less painful during removal which might be especially beneficial for a pediatric population [6]. The CE-mark of the Zip device was affixed in 2014 and the device is commercially available in Sweden today.

This clinical investigation is designed to evaluate the time and costs savings and the satisfaction and outcomes of the Zip device when used in a Pediatric emergency department setting for repair of lacerations in a pediatric population. Previous studies have mainly showed the benefits when using the Zip device on surgical incisions, both in adults and pediatric patients, but not in a pediatric population requiring laceration repair. The investigation subjects will be

randomized to receive either the Zip device or standard of care wound closure using sutures for 10 days. All subjects will be followed up for 30 days after treatment.

